- iii) Agents that modulate integrin pathways to impact lymphocyte trafficking (eg, natalizumab), or agents that modulate B cells or T cells (eg, alemtuzumab, abatacept, or visilizumab) within 3 months of Day 1
- iv) Rituximab within 6 months of Day 1

m) Has received systemic non-biologic psoriasis medications and/or any systemic immunosuppressants (including, but not limited to, methotrexate, azathioprine, cyclosporine, JAK inhibitors, 6-thioguanine, mercaptopurine, mycophenolate mofetil, hydroxyurea, tacrolimus, oral or injectable corticosteroids, retinoids, 1,25-dihydroxy vitamin D3 and analogues, psoralens, sulfasalazine, or fumaric acid derivatives) within 4 weeks prior to Day 1

- n) Has used leflunomide within 6 months prior to Day 1
- o) Has used opioid analgesics within 4 weeks prior to Day 1
- p) Has received lithium, antimalarials, or intramuscular (IM) gold within 4 weeks of the first administration of any study medication
- q) Has received phototherapy (including either oral and topical PUVA light therapy, ultraviolet B [UVB] or self-treatment with tanning beds or therapeutic sunbathing) within 4 weeks prior to Day 1
- r) Has used topical medications/treatments that could affect psoriasis evaluation (including, but not limited to, high potency corticosteroids (WHO Classes I-V), >3% salicylic acid, urea, alpha- or beta-hydroxyl acids, anthralin, calcipotriene, topical vitamin D derivatives, retinoids, tazarotene, methoxsalen, trimethylpsoralens, pimecrolimus, and tacrolimus) within 2 weeks prior to Day 1

Note: Low potency topical steroids (WHO Class VI and VII) are permitted on the palms, soles, face, and intertriginous areas but should not be used within 24 hours prior to any study visit. Bland emollients (defined as emollients without urea or alpha- or beta-hydroxy acids or other ingredients which are pharmacologically active) are allowed on all body regions but should not be used within 24 hours prior to any study visit.

- s) Use of shampoos that contain corticosteroids, coal tar, >3% salicylic acid, or vitamin D3 analogues within 2 weeks prior to Day 1
- t) Has received an experimental antibody or experimental biologic therapy within the previous 6 months, **OR** received any other experimental therapy or new investigational agent within 30 days or 5 half-lives (whichever is longer) prior to Day 1 **OR** is currently enrolled in an investigational study

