- Guidance and information for final disposition of unused study treatment are provided in [APPENDIX 2](#).

6.5.1 *Retained Samples for Bioavailability/Bioequivalence*

Not applicable.

6.6 *Treatment Compliance*

Study treatment compliance will be periodically monitored using standard drug accountability procedures (comparing the number of tablets returned to number dispensed, considering the expected regimen and any reported missed doses). Drug accountability will be reviewed by the investigative site staff at each visit to confirm treatment compliance. Site staff will discuss any discrepancies with the subject and remind the subject of the importance of compliance with the assigned regimen. A real-time monitoring platform may be used.

6.7 *Concomitant Therapy*

6.7.1 *Prohibited and/or Restricted Treatments*

Prohibited and/or restricted medications in the study are described below. Medications taken within 4 weeks prior to study drug administration must be recorded on the CRF.

- 1) Exposure to any investigational drug or placebo outside of the current study
- 2) Use of any medications/therapy that would aggravate psoriasis. These include agents such as lithium, antimalarials (quinacrine, chloroquine, and hydroxychloroquine), propranolol, indomethacin, and quinidine unless it is considered necessary for the subject's welfare and/or treatment of an AE/SAE
- 3) Use of opioid analgesics unless it is considered necessary for the subject's welfare and / or treatment of an AE/SAE
- 4) Phototherapy; use of tanning booths or therapeutic sunbathing
- 5) Any use of biologic medications (eg, adalimumab, etanercept, infliximab, ustekinumab)
- 6) Any use of oral psoriasis medications (eg, methotrexate, cyclosporine, retinoids, fumaric acid derivatives) for any indication
- 7) Any use of oral or injectable corticosteroids (prednisone, methylprednisolone, etc.), unless it is considered necessary for the subject's welfare and/or treatment of an AE/SAE
- 8) Note: otic, ophthalmic, nasal, or inhaled corticosteroids within recommended doses and with no systemic effects are permitted.
- 9) Any topical medications/treatments, which are used for any indication, that could affect psoriasis evaluation (including, but not limited to, high potency corticosteroids [WHO Classes I-V], >3% salicylic acid, urea, alpha- or beta-hydroxyl acids, anthralin, calcipotriene,

vitamin D derivatives, retinoids, tazarotene, methoxsalen, trimethylpsoralens, pimecrolimus, and tacrolimus)

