- Unblinding of a subject's treatment assignment for any reason (emergency or nonemergency)
- Inability or failure to comply with protocol requirements in the opinion of the investigator
- Loss of ability to freely provide consent through imprisonment or involuntary incarceration for treatment of either a psychiatric or physical (eg, infectious disease) illness

Refer to the Schedule of Activities ([Section 1.3](#)) for data to be collected at the time of treatment discontinuation and follow-up and for any further evaluations that can be completed.

All subjects who discontinue BMS-986165 should comply with protocol-specified follow-up procedures as outlined in Section 1.3. The only exception to this requirement is when a subject withdraws consent for all study procedures including posttreatment study follow-up or loses the ability to consent freely (ie, is imprisoned or involuntarily incarcerated for the treatment of either a psychiatric or physical illness). Replacement of subjects is not permitted.

If study treatment is discontinued prior to the subject's completion of the study, the reason for the discontinuation must be documented in the subject's medical records and entered on the appropriate eCRF page.

7.1.1 *Temporary Discontinuation of Study Medication*

Temporary study treatment discontinuation is allowed only if the subject develops an AE which, in the opinion of the investigator, indicates that it is in the subject's best interest that the study treatment be placed on hold. Study treatment in this situation should be stopped until the AE is medically treated and/or has resolved per PI judgement.

Any temporary study treatment discontinuation as well as restart must be documented on the corresponding eCRF.

7.1.2 *Post-Study Treatment Follow-up*

Post-study follow-up is of critical importance and is essential to preserving subject safety and the integrity of the study. Subjects who discontinue study treatment must continue to be followed for collection of outcomes and/or survival follow-up data as required and in line with [Section 4](#) until death or the conclusion of the study.

Subjects who discontinue study treatment should be encouraged to undergo the Week 52/Early Termination visit and the safety follow-up visit (Section 1.3) in order to support the final efficacy and safety analysis.

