9.6 Other Analyses

9.6.1 Demographics and Baseline Data

Demographics and baseline data will be summarized by treatment for each applicable analysis population. Categorical data will be summarized as frequency counts and percentages. Continuous data will be summarized using n, mean, standard deviation, median, minimum, and maximum unless otherwise specified.

9.6.2 *Prior and Concomitant Medications*

[figure not shown]
Prior and concomitant medications, categorized by medication group and subgroup according to the World Health Organization (WHO) Drug Dictionary, will be summarized by treatment for the As-treated population. Medications with an end date prior to the first dose of study drug will be considered prior medications.

9.6.3 *Relevant Protocol Deviations*

Relevant protocol deviations are deviations that can have an impact on the primary efficacy endpoints. The impact of relevant protocol deviations on the primary efficacy results will be assessed by excluding subjects from the FAS to define the PPS in supportive analyses of the primary efficacy endpoints. Relevant protocol deviations to be considered regarding exclusion of subjects from the FAS will include the following:

- Subject was randomized but did not take any study treatment
- Subject failed to meet any study inclusion criteria but was randomized to receive study treatment
- Subject met a study exclusion criterion which may have an impact on the coprimary efficacy endpoints but was randomized to receive study treatment
- Subject was noncompliant with study treatment within the first 16 weeks of treatment; defined as <80% compliant with study treatment
- Subject took prohibited concomitant medication prior to Week 16
- Subject received treatment different than assigned treatment at any visit prior to Week 16

All subjects with relevant protocol deviations will be identified prior to the Week 16 database lock. Relevant protocol deviations will be summarized by treatment group and deviation category for the FAS population.

9.7 *Interim Analyses*

No interim analysis is currently planned.

9.8 *Analysis and Reporting*

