2.5 Changes in Statistical Considerations from the Protocol

The following is a list of the important changes in the SAP from the Statistical Considerations section in the protocol:

- Endpoints are revised and 2-point improvement from baseline criterion is added to endpoints Static Physician's Global Assessment (sPGA), Scalp specific Physician's Global Assessment (ss-PGA), Physician's Global Assessment-Fingernails (PGA-F) and Palmoplantar Physician's Global Assessment (pp-PGA)
- The hierarchical testing order for the key secondary endpoints has been updated. The hierarchy presented here supersedes the one that is in the protocol.
- The two endpoints were removed from the list of key secondary endpoints: Change from baseline in Psoriasis Symptom and Sign Diary (PSSD) symptom score and Palmoplantar Physician's Global Assessment (pp-PGA) 0/1 assessed as a proportion of subjects with a pp-PGA score of 0 or 1 among subjects with a baseline pp-PGA score ≥ 3 .
- Imputation methods were updated to remove the prohibited medication/therapy criteria for binary and continuous endpoints.
- The list of relevant protocol deviations provided in the protocol was updated for determination of the Per Protocol population.
- Logistic regression analyses for binary endpoints were removed as these are similar to the CMH analyses.

• [REDACTED]
• [REDACTED]
• [REDACTED]
• [REDACTED]

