5.1 Relevant Protocol Deviations

Relevant protocol deviations are deviations that can have an impact on the primary efficacy endpoints. The impact of relevant protocol deviations on the primary efficacy results will be assessed by excluding subjects from the FAS to define the PPS in supportive analyses of the primary efficacy endpoints. Relevant protocol deviations to be considered regarding exclusion of subjects from the FAS will include the following:

- Randomized but did not take any study treatment
- No postbaseline PASI or sPGA
- Baseline BSA involvement < 10%
- Baseline PASI score < 12
- Baseline sPGA < 3
- Did not have plaque psoriasis at baseline
- Poor compliance to study medication within the first 16 weeks of treatment, <75% compliant with study treatment
- Failure to adhere to prohibited concomitant medication restrictions as described below:
 - Investigational drug or placebo taken outside of the study any time between Day 1 and the Week 16 assessment
 - Phototherapy within 4 weeks prior to the Week 16 assessment
 - Biologic medications (eg, adalimumab, etanercept, infliximab, ustekinumab) any time between Day 1 and the Week 16 assessment
 - Oral psoriasis medications any time between Day 1 and the Week 16 assessment
 - Oral corticosteroids (unless for the treatment of an adverse event) within 4 weeks prior to the Week 16 assessment
 - Topical medications/treatments that could affect psoriasis evaluations within 2 weeks prior to the Week 16 assessment
 - Medicated shampoos within 2 weeks prior to the Week 16 assessment
- Subject received treatment that was different than intended treatment at any visit prior to Week 16.

Sponsor: Bristol-Myers Squibb
Protocol no: IM011065

All subjects with relevant protocol deviations will be identified prior to Week 16 database lock and unblinding of treatment assignment for the analysis of data through Week 16 with the exception of subjects where actual treatment received is different than randomized treatment which will be determined after treatment unblinding. Relevant protocol deviations will be summarized by treatment group and deviation category for the FAS population.

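### SAP 5.1 removes oral but not injected corticosteroid users from the Per Protocol Set, although the protocol prohibits both routes

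*SAP*

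**What the plan says.** Protocol 6.7.1 item 7 prohibits "Any use of oral or injectable corticosteroids (prednisone, methylprednisolone, etc" and the rest of that bracket, except where needed for the subject's welfare or to treat an AE or SAE. Exclusion criterion 4m in protocol 5.2 also names the two routes together, "tacrolimus, oral or injectable corticosteroids, retinoids", in its list of systemic agents barred in the 4 weeks before Day 1. For the PPS, protocol 9.6.3 lists as a relevant deviation: "Subject took prohibited concomitant medication prior to Week 16".

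SAP 5.1 words this differently. Its criterion is "Failure to adhere to prohibited concomitant medication restrictions as described below", followed by a list. The corticosteroid entry in that list reads "Oral corticosteroids (unless for the treatment of an adverse event) within 4 weeks prior to the Week 16 assessment".

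SAP 2.5 discloses two related changes from the protocol: "The list of relevant protocol deviations provided in the protocol was updated for determination of the Per Protocol population", and "Imputation methods were updated to remove the prohibited medication/therapy criteria for binary and continuous endpoints". It gives no reason for a limit by route. SAP 5.0 makes the PPS a supportive population used for the coprimary endpoints only.

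**The concern.** The SAP's 4-week window before Week 16 has the same length as the entry washout in criterion 4m, but it covers only one of the two routes that the washout covers. Two subjects who take the same prohibited drug class in the same 4 weeks are then classified by route: the oral user leaves the PPS and the injected user stays.

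The PPS is the analysis meant to show what relevant deviations do to the coprimary results. Since prohibited therapy is no longer a trigger for non-responder imputation (NRI), an injected-steroid user who stays on study drug and attends Week 16 contributes an observed response to the Full Analysis Set (FAS). The PPS is where that subject would be set aside, and under the present line it does not do so. What is at stake is the accuracy of one supportive estimate and a membership rule that has to be applied before the Week 16 lock.

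**Working it through.** The plan states no figure on this point. The check is first a comparison of texts, then a sizing under assumptions.

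**1. Which rule catches a non-exempt injected corticosteroid in the 4 weeks before Week 16?**

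| Rule | Oral | Injected |
|---|---|---|
| Protocol 6.7.1 item 7 (prohibition) | yes | yes |
| Protocol 5.2, 4m (washout before Day 1) | yes | yes |
| Protocol 9.6.3 (any prohibited medication before Week 16) | yes | yes |
| SAP 5.1, corticosteroid line | yes | no |

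The other SAP 5.1 medication entries cover outside investigational drug, phototherapy, biologics, oral psoriasis medications, topical treatments and medicated shampoos. None describes an intramuscular or intravenous corticosteroid, and there is no catch-all entry. The subject stays in the PPS.

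**2. Which subjects does this leave?** Protocol 6.7.1 says the investigator should obtain the Medical Monitor's agreement before any concomitant medication is given. Protocol 7.1 requires study drug to be stopped for "Inability or failure to comply with protocol requirements in the opinion of the investigator", and under SAP 6.1.1.1 stopping before Week 16 gives NRI, which SAP 6.1.1.3 also applies in the PPS. The remaining case is an injection that is not for welfare or an AE/SAE, falls in the last 4 weeks, and does not lead to study drug being stopped.

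**3. Size per subject.** Assumptions:

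- The PPS is close to full size: 219 at 2:1 gives 219 × 2/3 = 146 and 219 × 1/3 = 73.
- Response rates equal the Phase 2 Week 12 rates in protocol 2.1 for 3 mg BID and placebo: PASI 75 68.9% and 6.7%, sPGA 0/1 75.6% and 6.7%.

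Responders: 0.689 × 146 = 100.6, taken as 101; 0.756 × 146 = 110.4, taken as 110; 0.067 × 73 = 4.9, taken as 5.

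Exclusion from the PPS takes a subject out of numerator and denominator. For one responder kept who should be excluded, the shift is x/n − (x − 1)/(n − 1):

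| Retained responder | Kept | Excluded | Shift (points) |
|---|---|---|---|
| Placebo, either endpoint | 5/73 = 6.85% | 4/72 = 5.56% | +1.29 |
| Active, PASI 75 | 101/146 = 69.18% | 100/145 = 68.97% | +0.21 |
| Active, sPGA 0/1 | 110/146 = 75.34% | 109/145 = 75.17% | +0.17 |

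**4. Direction.** The PASI 75 difference with the subject kept is 69.18 − 6.85 = 62.33 points. Excluding the placebo responder gives 69.18 − 5.56 = 63.62, so keeping that subject understates the effect. Excluding the active responder gives 68.97 − 6.85 = 62.12, so keeping that subject overstates it by 0.21.

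**5. Stress in the direction that favours the drug.** Suppose four of the active responders should have been excluded (four is an assumption). Then 97/142 = 68.31% replaces 69.18%, a shift of 0.87 points, and the PASI 75 difference is 68.31 − 6.85 = 61.46 points. Its unpooled standard error is √(0.6831 × 0.3169/142 + 0.0685 × 0.9315/73) = √(0.001524 + 0.000874) = 0.0490, so the ratio is 0.6146/0.0490 = 12.5.

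**The case against.** The strongest reply is that the narrowing was deliberate and declared. SAP 2.5 lists the revised deviation list among the important changes, and SAP 5.1 as a whole replaces any prohibited medication with selected items and windows, such as phototherapy within 4 weeks and topicals within 2. The PPS is therefore not meant to be free of every prohibited exposure, no entry carries a reason, and an entry washout does not bind a PPS definition. This stands as far as disclosure and the use of windows go. It does not explain a split by route within one drug class that item 7 and criterion 4m each treat as one.

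A second reply is that SAP 5.1 introduces its list with wording that could be read as non-exhaustive, and SAP 1.0 says the SAP is to be read with the protocol. However, the medication criterion limits itself to what is described below it. Deviations must be identified before the lock and unblinding, so the rule should not depend on interpretation.

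A third reply is that the case hardly arises. That is fair: the two safeguards in the working apply, and SAP 6.3.3 summarises concomitant medications by treatment group, so the use would still be visible.

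Two stronger readings are tempting, and the documents support neither. A reader might infer that the neighbouring line on oral psoriasis medications has the same fault, because injected methotrexate escapes it. That line matches the route in protocol 6.7.1 item 6, so it is not a departure by the SAP. A reader might also infer that the gap biases the trial towards the drug. SAP 5.1 does not affect the FAS primary analysis. In the PPS, the larger shift per retained responder is on placebo and works against the drug.

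**Conclusion.** The point holds as a minor inconsistency. SAP 5.1 keeps a non-exempt injected-corticosteroid user in the PPS and removes the oral counterpart, and nothing in either document justifies the difference. The effect is confined to the supportive PPS estimate: about 1.3 points on the placebo rate per retained placebo responder (conservative) and about 0.2 points on the active rate per retained active responder.

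These sizes assume a near-complete PPS and Phase 2 Week 12 rates that carry over to Week 16 at 6 mg QD. They also use sPGA 0/1 as reported in Phase 2, without the 2-point improvement that the SAP adds. The number of such subjects is not given and is probably small. The superiority conclusion is not at risk: it rests on the FAS, and even the assumed stress case leaves a PPS difference above 61 points.

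**What to change.** Before the Week 16 database lock, reword the corticosteroid line in SAP 5.1 along these lines: *oral or injectable corticosteroids in the 4 weeks before the Week 16 assessment, unless needed for the subject's welfare and/or to treat an AE or SAE*. This adds the missing route and brings the exemption into line with protocol 6.7.1 item 7. At present the SAP exempts AE treatment only, so adding the route without the fuller exemption would exclude subjects whose injection the protocol allows.

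Leave the oral psoriasis medications line as it is. Widening it to injectables would go beyond item 6. Because criterion 4m puts corticosteroids in the same list as systemic psoriasis drugs and immunosuppressants, a wider line could also be read to cover corticosteroids with no exemption and no window.

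The cost is one line in the SAP, applied to concomitant medication data already collected, with no protocol amendment. The PPS may lose a few injected users, and an oral user treated for welfare reasons would no longer be excluded. If the sponsor does intend the oral-only rule, a sentence giving the reason would be enough.

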6.0 Statistical Analyses

Descriptive summaries and analyses outlined in [Appendix 1](#) will be presented for data captured throughout the study using the following treatment groups.

For the comparison of endpoints collected during the first 16 weeks of treatment, summaries will be provided for the following treatment groups:

- BMS-986165 6 mg QD
- Placebo

After Week 16, data will be presented for the following treatments:

- BMS-986165 6 mg QD (starting from Week 16 through Week 52)
- Subjects who switched from placebo to BMS-986165 6 mg QD (including Week 16 through Week 52)
- All BMS-986165 6 mg QD (all subjects exposed to BMS-986165 6 mg QD; includes subjects on placebo that switched to BMS-986165 6 mg QD)

6.1 Efficacy Analyses

All efficacy analyses will be performed using the FAS, unless otherwise specified.

Tests to compare BMS-986165 6 mg QD vs. placebo for the coprimary endpoints will be two-sided with a significance level of 0.05. If both coprimary endpoints are statistically significant then testing will proceed for the secondary family of key secondary endpoints. In order to control for Type I error rate inflation within the secondary family of key secondary endpoints, a hierarchical testing method will be implemented for the key secondary endpoints.

The key secondary endpoints will be tested with a two-sided significance level of 0.05 to compare BMS-986165 6mg QD vs. placebo. A hierarchical testing approach will be used for testing of key secondary endpoints (see [Section 6.1.3](#)). If an endpoint fails at any step, then all subsequent p-values will be considered descriptive. Two-sided 95% confidence intervals (CIs) will be provided for all efficacy estimates. [REDACTED]

6.1.1 Primary Endpoints

6.1.1.1 Primary Analysis

Analysis Model

A stratified Cochran-Mantel-Haenszel (CMH) test will be used to compare the sPGA 0/1 response rates at Week 16 between BMS-986165 6 mg QD and placebo. The following stratification factors from IRT are included in the model: country (mainland China, non-mainland China) and prior biologic use (yes/no). The odds ratio (ratio of odds in BMS-986165 6 mg QD group to the odds in the placebo group) and the corresponding 2-sided 95% CIs and p-values

Sponsor: Bristol-Myers Squibb
Protocol no: IM011065

will be reported. Additionally, treatment differences in proportions and the 95% CI for the treatment difference will be provided. The common treatment difference in proportion with the confidence interval, common odds ratio with the 2-sided 95% confidence interval and p-value will be estimated by the Mantel-Haenszel method consistently.

Similar analyses will be performed to compare the PASI 75 response rates at Week 16 between BMS-986165 6mg QD and placebo.

Imputation Methodology

Non-responder imputation (NRI) will be used for coprimary efficacy endpoints for subjects who:

- Discontinue treatment or study prior to Week 16
- Have missing Week 16 endpoint data for any reason

NRI will be used as the primary method of imputation for the coprimary efficacy endpoints.

